2.2 Primary Outcome Measures

The changes of dyskinesia scores (UPDRS IV, item 32 + item 33) in interleaving stimulation compared to empirical programming modes. *[Time Frame: 3 months and 9*

months]

The changes of Parkinson's disease quality of life-39 (PDQ-39) scores in interleaving stimulation compared to empirical programming modes. *[Time Frame: 3 months and 9 months]*

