4.1 Efficacy assessments

The primary efficacy endpoints are the changes of dyskinesia scores and the changes of PDQ-39 scores in interleaving stimulation compared to empirical programming modes. *[Time Frame: 3 months and 9 months]*

The secondary endpoints include the changes of UPDRS III scores and the changes of neuropsychological Battery scores in interleaving stimulation compared to empirical programming modes. *[Time Frame: 3 months and 9 months]*

The parameters in primary and secondary endpoints are also tested at baseline (Enrollment). After DBS activation (Month 0), patients are again assessed at Month 3, Month 9 and Month 12 in off-medication/on-stimulation and on-medication/on-stimulation, as shown in table 1. We defined “on-medication” as roughly 60 min after a patient takes

antiparkinsonian medication when both the clinician and the patient indicate that the medication dose is effective.

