5.1 Sample size

According to the sample size estimation method of comparing the mean of two independent samples, 42 subjects are planned to be enrolled in this study. Increase the number of cases according to the 20% dropout rate, and finally enrolled 50 cases. In this study, the change scores of total scores of visit 5 (month 12) UPDRS IV comparation with baseline is the endpoint to use to calculate the sample size. The specific calculation method was as follows:

Use Power Analysis & Sample Size software 11 (SPSS 11) to calculate the sample size. The formula is as follows.

$$n = \text{Ceiling} \left\{ \frac{(Z_{1-\alpha} + Z_{1-\beta})^2 \sigma_d^2}{2\delta_1^2} \right\}.$$

The non-inferiority hypothesis

Primary Outcome Measures

The changes of dyskinesia scores (UPDRS IV, item 32 + item 33)

H0: interleaving stimulation - empirical stimulation < 0.5 score

H1: interleaving stimulation - empirical stimulation \geq 0.5 score

Significance level: $\alpha = 0.025$ (unilateral),

Power: $1-\beta = 0.8$,

Standard deviation of single group: SD = 1.1,

H0 is the null hypothesis, H1 is the alternative hypothesis. After subjects receiving interleaving stimulation, if the mean change scores of UPDRS IV equals or exceeds 0.5 points than that of those patients receiving empirical stimulation, then H0 will be rejected, non-inferiority conclusion can be made when comparing interleaving stimulation group with empirical stimulation group. If H0 can't be reject, the conclusion that the interleaving stimulation group is better than or equivalent to empirical stimulation group can't be reached.

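### Section 5.1 does not tie its 80% power and 0.5-point rule to one score and visit: it names total UPDRS IV at Month 12, then items 32+33 with no visit, while the primary dyskinesia outcome is items 32+33 at 3 and 9 months

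*Combined protocol and SAP*

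**What the plan says.** Section 5.1 (Sample size) states that the "change scores of total scores of visit 5 (month 12) UPDRS IV comparation with baseline is the endpoint" for the calculation, and that "42 subjects are planned to be enrolled in this study", raised to 50 for dropout. Further down, under the label "The non-inferiority hypothesis" and a line naming the primary outcome as items 32+33 of UPDRS IV, it gives "H0: interleaving stimulation - empirical stimulation < 0.5 score", one-sided alpha 0.025, power 0.8 and a single-group SD of 1.1. No visit is attached to these figures. The closing decision sentence of 5.1 speaks only of the mean change in UPDRS IV.

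Section 2.2 defines the first primary outcome as "The changes of dyskinesia scores (UPDRS IV, item 32 + item 33) in interleaving stimulation compared to empirical programming modes". Section 4.1 repeats that "The primary efficacy endpoints are the changes of dyskinesia scores and the changes of PDQ-39 scores in interleaving stimulation compared to empirical programming modes" and adds "Time Frame: 3 months and 9 months". It names enrolment as baseline and schedules assessments at Months 3, 9 and 12.

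Sections 3.1 and 3.2 fix the treatment periods. Both arms receive empirical stimulation, with no interleaving, to Month 3. From Month 3 to Month 9 the arms differ by assigned mode, and the mode is held. After Month 9 either arm may receive any mode.

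**The concern.** A power statement means something only for a named score, baseline, visit and assumed difference. Section 5.1 offers two scores (total UPDRS IV, and items 32+33), and the only visit it names lies outside the primary outcome's time frame. The 0.5-point rule is the only decision rule in the document, and its wording does not say which score or visit it applies to.

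The visit matters because of the design. At Month 3 the modes have not yet diverged. At Month 12 both arms have had three months of unrestricted programming, so a comparison there estimates the effect of the assigned sequence and not of the assigned mode. If the 0.5-point rule were applied at Month 12 as a non-inferiority test, any convergence of the arms after Month 9 would make it easier to pass. Section 5.2 (Statistical analysis) does not settle the matter, because it names no primary score, visit or model.

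**Working it through.** **Step 1: the statements side by side.**

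| Place | Score | Visit |
|---|---|---|
| 5.1, sizing sentence | Total UPDRS IV | Month 12, change from baseline |
| 5.1, hypotheses, alpha, power, SD, 0.5 | Items 32+33 | None |
| 5.1, decision sentence | UPDRS IV, unspecified | None |
| 2.2 | Items 32+33 | 3 and 9 months |
| 4.1 | Dyskinesia scores | 3 and 9 months |
| 5.2 | None | None |

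**Step 2: the visits against the treatment periods (3.1, 3.2).** Month 3 ends a period in which the arms have the same mode. Month 9 ends the six months in which they differ. Month 12 ends three months in which the mode is free in both arms. Only Month 9 closes the randomised contrast, and Table 1 already schedules UPDRS IV there (V4).

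**Step 3: the plan's own 42.** Inputs from 5.1: 0.5 points, SD 1.1, one-sided 0.025, power 0.8.
- Printed formula, normal version: (1.960 + 0.842)² × 1.1² / (2 × 0.5²) = 7.849 × 1.21 / 0.5 = 18.99. That is 19 per sequence, or 38 in total.
- Noncentral-t version of the same crossover-type formula: noncentrality = 0.5 × √N / 1.1 with N − 2 degrees of freedom. N = 40 gives power 0.79997, and N = 42 gives 0.820. This reproduces 42.
- No step uses anything specific to total UPDRS IV or to Month 12. If 0.5 and 1.1 already describe items 32+33 at Month 9, relabelling the endpoint leaves 42 unchanged.

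**Step 4: what 42 gives in the design described (two independent groups).** SE = 1.1 × √(2/n). Power = P(noncentral t > t at 0.975), with noncentrality = distance to the tested bound / SE and 2n − 2 degrees of freedom. For n = 21, SE = 0.3395 and the critical t is 2.021. For n = 25, SE = 0.3111 and the critical t is 2.011.

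| Distance to bound | 21 per arm | 25 per arm |
|---|---|---|
| 0.5 | 30% | 35% |
| 0.75 | 58% | 66% |
| 1.0 | 82% | 88% |

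The 82% needs a distance of 1.0 point, for example a 0.5-point margin plus a true benefit of 0.5. The documents state no such benefit.

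**Step 5: a conditional illustration of the visit.** Assumptions: the 0.5-point test is run at Month 12, 0.5 is a non-inferiority margin, SD is 1.1, n is 21 per arm, and a fraction f of the Month 9 difference is lost by Month 12. Suppose that interleaving is 0.5 points worse at Month 9. The Month 12 difference is then 0.5 × (1 − f), which lies 0.5 − 0.5 × (1 − f) = 0.5f inside the margin.

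| f | Distance inside margin | Noncentrality | Chance of concluding non-inferiority |
|---|---|---|---|
| 0 | 0 | 0 | 2.5% |
| 0.25 | 0.125 | 0.368 | 5.5% |
| 0.50 | 0.25 | 0.736 | 10.7% |

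The documents give no switching rate, so f is assumed and could be nil.

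**The case against.** The strongest reply is that the Month 12 phrase is a misplaced sizing label. Alpha, power, SD and the 0.5 points all stand under a line naming the primary outcome and items 32+33, and 2.2 and 4.1 give that outcome its time frame. Much of this stands. A reader might infer that the 80% power belongs to the wrong endpoint, but the text does not go that far: the figures cannot be assigned to either score or to a visit.

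A reader might also infer that the planned analysis carries an inflated risk of false non-inferiority. The documents do not support that. Month 12 is named only for sizing, and 5.2 plans no test there. Free choice of mode after Month 9 also allows the assigned mode to be kept. And with 25% of the difference lost, the Month 12 difference is 0.375 points, which is truly inside a 0.5 margin. The conclusion is wrong only if it is carried back to Month 9.

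Finally, the time frame of 3 and 9 months may mean change from Month 3 to Month 9. On that reading Month 3 is a reference and not a second test. Month 9 is still the endpoint visit, so the reading does not rescue Month 12.

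**Conclusion.** The contradiction is in the current text, both within 5.1 and between 5.1 and sections 2.2 and 4.1. It must be resolved, because the power claim and the only decision rule are not tied to one score and visit. Confidence in the contradiction is high. Its numerical effect can only be bracketed.

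Two stronger conclusions should not be drawn. The mismatch does not by itself show that 42 is wrong: no separate SD or difference is given for either score or visit, and the use of a crossover-type formula for two independent groups is a separate question. Nor does moving to Month 9 by itself secure 80% power. The only difference stated, 0.5 points with SD 1.1, gives about 30% with 21 per arm and 35% with 25 per arm if it is the distance to the tested bound. The 5.5% and 10.7% figures hold only under every condition in step 5, including reading 0.5 as a non-inferiority margin. The heading in 5.1 suggests that reading, but the printed hypotheses do not express it clearly.

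**What to change.** - **5.1:** replace total UPDRS IV at visit 5 (Month 12) with UPDRS IV items 32+33 at visit 4 (Month 9), and use that score and visit in the hypotheses and the decision sentence.
- **2.2 and 4.1:** state whether change runs from enrolment or from Month 3. State that Month 3 precedes the mode contrast and is not a second test of it.
- **Inputs:** confirm that SD 1.1 and 0.5 points apply to that score and visit, and state the assumed true difference.
- **Power:** restate the power of 42 evaluable (50 enrolled) patients for a comparison of two independent groups.
- **Month 12:** label any comparison there as the effect of assigned sequence.

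The cost is wording in three sections and one recalculation. No visit is added, because Table 1 already collects UPDRS IV at Month 9. The downside is that the restated power may be well below 80%, and the sponsor would then have to address that openly.

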2.4 Safety outcome Measures

Adverse events *[Time Frame: up to 12 months]*

Any adverse medical event from date of randomization until the date of first documented adverse event or date of death from any cause, which ever comes first, assessed up to 12 months.

Persistent dyskinesia despite optimization of parameters of stimulation is defined with severity ≥ 2 on item 32 and duration ≥ 2 (e.g., duration \geq up to 50% of the 16 hours ambulatory time) on item 33 of the unified Parkinson's disease rating scale (UPDRS) part IV.

2.5 Study population:

Indications of DBS for PD consistent with the China specific approved labeling.

Inclusion Criteria

- Patients at the age of 30–65 years old.
- Patients diagnosed as Parkinson's disease according to the UK Parkinson's Disease Society Brain Bank criteria.
- Patients at Hoehn and Yahr stage 3 or lower in the on-state and stage 2 - 4 in the off-state.
- The disease duration of 5 years or more.
- Patients with deep levodopa-responsive Parkinson's disease, and are not adequately controlled by drug therapy.

Study participants will be PD patients undergoing DBS of the subthalamic nucleus (STN). Whether or not a patient is selected for DBS surgery is determined by the patient's clinical team purely on independent clinical grounds. Only those patients who have been accepted for DBS treatment by their clinical neurologist and functional neurosurgeon will

be introduced to the project and have their details passed on to the research team for further information and formal informed consenting.

Exclusion Criteria

Exclusion criteria are: major illness or medical comorbidities, depression that is untreated but judged to be clinically significant by an investigator, cochlear implants, cardiac pacemakers, needs for diathermy, anticoagulant therapy, previous neuro-surgical procedure or ablative therapy, frank dementia according to cognitive screening, drug or alcohol abuse, being a woman of child-bearing potential, having a positive pregnancy test, or presence of a terminal illness.

Written informed consent is obtained from all patients before any study procedures were started.

3. Study Process

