5.2 Statistical analysis

All of the statistical tests used bilateral analysis. $P \leq 0.05$ is considered to be statistically significance (excluding special conditions).

Description of quantitative indicators is used to calculate total cases, missing cases, average cases, standard deviation, minimum, maximum, median and the interquartile range.

Description of classification index is used in different groups of cases and percentage.

Full Analysis Set (FAS): this analysis includes all subjects who received any treatment and provided useful value after the baseline stage for analysis. It also includes violators of the research scheme and subjects with incomplete data who left the trial.

Per Protocol Set (PPS): this analysis includes all subjects who completed the research and complied with the scheme without any serious errors. It also includes subjects who quit the trial because of ineffective treatment.

Safety Analysis Set (SAS): this analysis set includes all subjects who enrolled in the trial, received at least one treatment and was used for safety evaluation. Safety information records from all subjects were evaluated, including adverse events and the results of lab examinations.

6. Adverse Event

6.1 definition

Adverse Event : An AE is defined as any untoward medical occurrence, regardless of its relationship to the study device (study suture) or the study procedure. An untoward medical occurrence includes any new, undesirable medical experience or worsening of a pre-existing condition, which occurs at any point from the surgery to Final Visit.

Serious Adverse Event: A Serious Adverse Event (SAE) is any AE that:

- led to a death,
- led to a serious deterioration in the health of the subject that either resulted in:
 - a congenital deformity or abnormality;
 - a life-threatening illness or injury;
 - a permanent impairment of a body structure or a body function;
 - in-patient hospitalization or prolongation of existing hospitalization;
 - medical or surgical intervention to prevent life-threatening illness or injury; or permanent impairment of a body structure or a body function.

Relationship of Adverse Events: It is the Investigator's responsibility to assess the relationship of an AE to the study procedure and study device.

The following guidelines should be used in determining the relationship of an adverse event

to the study device, study procedure, or other causality:

- NOT RELATED: The event is due to extraneous causes.

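### Section 5.1's non-inferiority hypotheses place true equality in the null and leave the sign of change undefined, so the rule as written does not test non-inferiority

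*Combined protocol and SAP*

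**What the plan says.** Section 5.1 of the combined protocol and SAP gives one pair of hypotheses, for the change in UPDRS IV items 32 + 33, under a non-inferiority label. The null is "H0: interleaving stimulation - empirical stimulation < 0.5 score" and the alternative is a difference of at least 0.5. The text then puts the rule in words: if the interleaving group's "mean change scores of UPDRS IV equals or exceeds 0.5 points than that of those patients receiving empirical stimulation, then H0 will be rejected", and non-inferiority may be concluded. If the null is not rejected, "the conclusion that the interleaving stimulation group is better than or equivalent to empirical stimulation group" cannot be reached.

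The same section sets one-sided alpha 0.025, power 0.8 and a single-group SD of 1.1. It describes the calculation as "comparing the mean of two independent samples, 42 subjects are planned to be enrolled in this study", raised to 50 for dropout. The endpoint named for sizing is "the change scores of total scores of visit 5 (month 12) UPDRS IV comparation with baseline", which is neither the item sum nor the 3- and 9-month time frame of section 2.2.

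Section 5.2 adds "All of the statistical tests used bilateral analysis" and a 0.05 threshold, with no null value, margin or direction. Nothing in the document defines the sign of change. The direction of the scale itself can be read from section 2.4: "Persistent dyskinesia despite optimization of parameters of stimulation is defined with severity ≥ 2 on item 32 and duration ≥ 2", so higher is worse.

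**The concern.** A non-inferiority null should contain inferiority by the margin or more, and the alternative should contain equality. Here 0 is below 0.5, so equal arms satisfy the null whichever way change is signed. What rejection means then depends on a convention that the plan does not give.

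- **Positive = improvement.** The alternative is that interleaving is better by at least 0.5. That is superiority by a margin.
- **Positive = worsening (follow-up minus baseline).** The alternative is that interleaving is worse by at least 0.5, yet rejecting the null is said to show non-inferiority.

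The sentence in words adds a third possibility. It rejects on the observed mean difference alone, with no allowance for sampling error. These are the only hypotheses stated for either primary endpoint, so they decide what the trial may claim. Left open, the choice among the three rules could be made after the data are seen.

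**Working it through.** **Inputs.** From section 5.1: margin 0.5, SD 1.1, one-sided alpha 0.025, power 0.8, 42 evaluable, 50 enrolled, 20% dropout. From section 3.1: 25 per arm, 1:1. I take n per arm as 20 (25 × 0.8), 21 (42/2) and 25 (no dropout). *Assumption:* SD 1.1 applies per arm to the change in items 32 + 33.

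**1. The plan's own 42.** The printed formula, taking its SD as 1.1 and its delta as 0.5, gives (1.960 + 0.842)² × 1.1² / (2 × 0.5²) = 18.99, so 19, not 42. Two t-based calculations do give 42:

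- The printed crossover-type form with t: SE = 1.1/√(2n), df = 2n − 2, distance 0.5. Noncentrality = 0.5√(2n)/1.1 = 0.643√n.
- Two parallel arms: SE = 1.1√(2/n), df = 2n − 2, distance 1.0 between null and assumed truth (for example margin −0.5 and true benefit +0.5). Noncentrality = 1.0/(1.1√(2/n)) = 0.643√n.

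The two are identical in noncentrality and df. Both have power 0.79997 at n = 20 and 0.820 at n = 21, hence 21 per group and 42 in total. For comparison, two parallel arms with margin 0.5 and true equality need 2 × (1.960 + 0.842)² × 1.1² / 0.5² = 75.98, so 76 per arm (77 by t).

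**2. Formal test, written against correct.** SE = 1.1√(2/n) and half-width h = t(0.975, 2n − 2) × SE. With improvement positive, the written test needs an observed advantage of 0.5 + h. A correct 0.5-margin test needs h − 0.5. Success probabilities use the noncentral t with noncentrality (true benefit − 0.5)/SE for the written test and (true benefit + 0.5)/SE for the correct one.

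| | n = 20 | n = 21 | n = 25 |
|---|---|---|---|
| SE | 0.348 | 0.339 | 0.311 |
| h | 0.704 | 0.686 | 0.626 |
| Observed advantage needed, written | 1.204 | 1.186 | 1.126 |
| Observed advantage needed, correct | 0.204 | 0.186 | 0.126 |
| Written, true benefit 0 | 0.04% | 0.03% | 0.02% |
| Correct, true benefit 0 | 28.8% | 30.1% | 35.0% |
| Written, true benefit 0.25 | 0.39% | 0.37% | 0.30% |
| Correct, true benefit 0.25 | 55.6% | 57.8% | 65.6% |
| Written, true benefit 0.5 | 2.5% | 2.5% | 2.5% |
| Correct, true benefit 0.5 | 80.0% | 82.0% | 88.3% |

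A trial that passes the written test also passes the correct one. The share lost to the wording at a true benefit of 0.5 is therefore 80.0 − 2.5 = 77.5% to 88.3 − 2.5 = 85.8%.

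**3. Opposite coding.** With follow-up minus baseline, the written rows apply to true harm. Non-inferiority is declared in 2.5% of trials at a harm of 0.5, 29–35% at 1.0 and 80–88% at 1.5.

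**4. Prose applied to observed means.** P(observed ≥ 0.5) = 1 − Φ((0.5 − true)/SE). At a true difference of 0 this is 7.5%, 7.0% and 5.4% for n = 20, 21 and 25. At a true difference of 0.5, the boundary of the null, it is 50%, not 2.5%. That 0.5 is benefit or harm according to the coding.

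**5. Sensitivity to the SD.** At an assumed SD of 1.5, the correct test's power is 18–21% at equality and 54–64% at a benefit of 0.5. The written test stays at 2.5% at 0.5 by construction.

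**The case against.** The strongest reply is that a minus sign was dropped. With improvement coding and a null of less than −0.5, the pair becomes a standard non-inferiority test. The two-arm route to 42 with distance 1.0 fits that idea, and it matches the section's references to independent samples and a single-group SD. This may be what was meant. It does not rescue the text, because the prose separately repeats the +0.5 threshold and would then contradict the hypotheses.

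A second reply is that under the favoured coding the error is only conservative. That stands: a positive result would imply non-inferiority, and no false claim arises. The cost is a conclusion withheld.

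A third is that the aim in sections 1 and 2.1 is to assess differences, and 5.2 specifies two-sided tests, so non-inferiority may not be the real question. That also stands, and it supports a second form of repair. It does not supply a null value or direction for the rule in 5.1.

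Three stronger inferences are tempting, and the documents do not support them:

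- **The plan fails in 97% of trials at a true benefit of 0.5.** That holds only for the formal test with improvement coding. The prose rule fails in 50%, and a correct test would itself fail in 12–20%.
- **The 42 came from a crossover formula, so its 80% power does not apply here.** The two-arm route fits equally well and the documents state no assumed benefit, so the origin cannot be settled.
- **The plan sets out to label harm as non-inferior.** That needs the less likely coding. The closing sentence treats rejection as the favourable outcome.

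**Conclusion.** The decision rule is wrong as written and must be corrected. Equality lies in the null under either coding, the sign of change is undefined, and section 5.2 does not repair it. Under improvement coding the trial would be held to superiority by 0.5 points, needing an observed advantage of about 1.13–1.20 instead of 0.13–0.20. Under the other coding only harm yields the claim. Applied to observed means, the prose does not control alpha at 0.025 at the boundary.

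That the null is misplaced and the sign missing depends on no assumption. The percentages do: they rest on SD 1.1 for the change in items 32 + 33, normal data, and 20 to 25 per arm. The plan's sizing text names a different endpoint, so the SD is uncertain.

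A reader might also infer that the trial must be enlarged. That does not follow. With 42 evaluable, a correct 0.5-margin two-arm test has about 80% power if a true benefit of about 0.5 is assumed, and about 30% if the arms are equal. The plan must say which it assumes.

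**What to change.** In section 5.1:

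1. Define D = mean(ISG) − mean(ESG) in the change of items 32 + 33, follow-up minus baseline, higher = worse, at month 9. Under sections 3.1 and 3.2, this is the visit that compares the assigned modes. Reconcile it with the month-12 total UPDRS IV wording. Name the baseline; section 4.1 uses enrolment ("The parameters in primary and secondary endpoints are also tested at baseline (Enrollment").
2. State H0: D ≥ +0.5 against H1: D < +0.5.
3. Conclude non-inferiority only if the upper limit of the two-sided 95% confidence interval for D is below +0.5. Then, in fixed order, conclude superiority if that limit is below 0.
4. Delete the sentence that rejects the null on the observed mean change, and have section 5.2 cite this rule.
5. Restate the power for the chosen test, with the true difference it assumes and a justification of the SD for that endpoint and baseline.

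If the sponsor's aim is only to detect a difference, as sections 1 and 2.1 suggest, the alternative is to delete the non-inferiority wording and state a two-sided difference hypothesis, again with its power.

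The cost is a protocol/SAP amendment and possibly a less favourable stated power. The fixed order spends no extra alpha within this endpoint. No new data, visits or patients are required.

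### The written success rule for the dyskinesia primary compares the observed mean difference with 0.5 and uses no confidence limit, so it does not have the stated one-sided 2.5% error rate

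*Combined protocol and SAP*

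**What the plan says.** Section 5.1, under its non-inferiority heading, takes the change in UPDRS IV items 32 and 33 as the outcome. It prints the null as "H0: interleaving stimulation - empirical stimulation < 0.5 score" and the alternative as a difference of 0.5 or more. The design inputs beside it are a one-sided alpha of 0.025, power of 0.8 and "Standard deviation of single group: SD = 1.1".

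The decision rule follows: "mean change scores of UPDRS IV equals or exceeds 0.5 points than that of those patients receiving empirical stimulation, then H0 will be rejected". The claim attached to that rejection is that a "non-inferiority conclusion can be made when comparing interleaving stimulation group with empirical stimulation group". The next sentence says what may not be concluded if H0 stands. Together the two sentences read as a complete rule for success and failure.

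Section 5.2 says "All of the statistical tests used bilateral analysis" and gives P ≤ 0.05 as the general threshold, with an undefined exception for special conditions. It names no test, model or null value for the dyskinesia endpoint and does not mention 0.5. No confidence interval appears anywhere in the document.

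On numbers, Section 5.1 says "42 subjects are planned to be enrolled in this study", then "Increase the number of cases according to the 20% dropout rate, and finally enrolled 50 cases". Section 3.1 allocates 1:1.

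**The concern.** A hypothesis about a true difference cannot be tested at a chosen level by asking only whether the observed difference has reached the hypothesised bound. If the true difference sits on that bound, the observed one falls on either side about equally often, whatever the sample size or SD. The printed rule makes no allowance for sampling error, so the alpha of 0.025 printed above it plays no part in the decision.

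This is the only rule tied to the 0.5-point bound for one of the two primary outcomes, and it decides whether the trial may claim non-inferiority. An analyst who follows it literally declares success on the point estimate. One who does not must choose the test, the null value and the sidedness without guidance, possibly after seeing data.

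**Working it through.** **Inputs.** From Section 5.1: bound 0.5, SD 1.1, one-sided alpha 0.025, power 0.8, 42 evaluable and 50 enrolled. With 1:1 allocation (Section 3.1) that is 21 or 25 per arm. Section 5.1 states no assumed true difference, so a range is shown. It also sizes the trial on total UPDRS IV at Month 12 while the hypotheses concern items 32 and 33, so applying SD 1.1 to the latter is an assumption.

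**1. The plan's own sample size.**
- Printed formula: (1.960 + 0.8416)² × 1.1² / (2 × 0.5²) = 7.849 × 1.21 / 0.5 = 18.99, or 19.
- The same crossover-type formula iterated with the t distribution gives 41 in total, or 42 for equal groups.
- A two-sample t calculation gives 21 per arm if the truth lies 1.0 from the bound, a distance the plan does not state.
- Two independent arms with the truth 0.5 from the bound: 2 × 1.21 × 7.849 / 0.25 = 75.98, or 76 per arm (77 with t).
- Dropout: 42 × 1.2 = 50.4, close to the 50 stated.

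How 42 was reached is a separate matter. What counts here is that the printed formula contains an alpha term, which a rule on the point estimate would not need.

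**2. Standard error.** SE = 1.1 × √(2/n): 0.3395 with 21 per arm, 0.3111 with 25.

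**3. The rule as written.** P(reject | true difference d) = 1 − Φ((0.5 − d)/SE). For example, with d = 0 and 21 per arm, 0.5/0.3395 = 1.473 and 1 − Φ(1.473) = 0.070.

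| True difference | 21 per arm | 25 per arm |
|---|---|---|
| +0.5 | 50.0% | 50.0% |
| +0.25 | 23.1% | 21.1% |
| 0 | 7.0% | 5.4% |
| −0.5 | 0.16% | 0.07% |

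Simulation of 200,000 trials gave 50.1% at +0.5 for both sizes. Under the printed H0, the error approaches 50% as the truth approaches +0.5 from below. Under an assumed margin of −0.5, with change scored as improvement, the last row is the error at the boundary and the row for 0 is the power when the arms are equal.

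**4. A confidence-limit rule.** The observed difference must reach the bound plus t × SE, with t = 2.021 on 40 df or 2.011 on 48 df.
- Bound +0.5: 0.5 + 2.021 × 0.3395 = 1.19 (21 per arm); 0.5 + 2.011 × 0.3111 = 1.13 (25 per arm). Simulated error at the bound is 2.52% and 2.45%. The true difference needed for 80% power is 0.5 + 2.8016 × SE = 1.45 or 1.37.
- Bound −0.5: −0.5 + 0.686 = +0.19 (21 per arm); −0.5 + 0.626 = +0.13 (25 per arm). Power at a true difference of 0 is Φ(0.5/SE − 1.96) = 31% or 36%.

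**5. Whether Section 5.2 fills the gap.** A default two-sided 0.05 test of zero difference needs an observed difference of 2.021 × 0.3395 = 0.69 (21 per arm). An observed 0.6 would pass the rule in 5.1 and fail that test. The two sections therefore do not give one rule, and a null of zero is neither +0.5 nor −0.5.

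**The case against.** The strongest reply is about context. The sentence sits in the sample-size section, just below the stated alpha and power, and the formula uses the alpha quantile. It can be read as a loose paraphrase of H1, with rejection at one-sided 0.025 taken for granted. The exception in Section 5.2 may also leave room for a one-sided primary test. As a view of intent, this stands. A reader might infer that the trial will run with a 50% false-positive rate, and the documents do not support that. But the reply does not remove the contradiction, because the printed rule has no place for alpha and no test is named elsewhere.

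The second reply is that the 50% depends on the boundary being +0.5, and that any point-estimate cut-off has 50% error at its own boundary. This also stands. A reader might infer that the rule is too lenient whichever direction was meant. It is not: against −0.5 it is very conservative. At the planned SD with 21 per arm, an observed 0.5 has a lower limit of 0.5 − 0.686 = −0.19, which already excludes −0.5. On that reading equal arms satisfy non-inferiority, so 7.0% and 5.4% are low power and not error rates.

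The third is that direction is the main fault. Section 2.4 defines persistent dyskinesia by high item scores, so if change means follow-up minus baseline, +0.5 would favour empirical stimulation. Direction must indeed be settled. Correcting the sign alone is not enough, because a point-estimate cut-off moved to −0.5 has 50% error at −0.5.

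**Conclusion.** The rule is wrong as written and needs correcting before analysis. It does not have the one-sided 2.5% error rate that Section 5.1 states, under either direction of the margin. On the literal +0.5 boundary the error reaches 50% at the boundary. On an assumed −0.5 margin it is about 0.16% (21 per arm) or 0.07% (25 per arm), and the trial would succeed only about 5–7% of the time with equal arms.

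The 50% at the literal boundary needs only a symmetric sampling distribution. The other figures rest on SD 1.1, approximate normality and 21 or 25 analysed per arm. The finding is a contradiction between the printed rule and the stated alpha. It does not forecast how the analysis will be run.

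**What to change.** In Section 5.1, first state the sign of the change score (whether positive means improvement) and the sign and direction of the 0.5-point margin. Then replace the decision sentence with:

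> H0 is rejected only if the two-sided 95% confidence interval (one-sided alpha 0.025) for the between-arm difference in change in item 32 + item 33 at Month 9 lies entirely on the favourable side of the margin. The observed mean difference alone does not decide.

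Repeat this rule in Section 5.2 for this endpoint, in place of the general P ≤ 0.05, and name the model that yields the interval.

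Month 9 is proposed because it lies in the primary time frame of Sections 2.2 and 4.1 and ends the randomised stimulation period (Sections 3.1 and 3.2). Month 3 precedes interleaving, and after Month 9 the mode is free in both arms. The Month 12 total UPDRS IV endpoint used for sizing must be reconciled with it.

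The drafting cost is a sentence or two in each section. The effect on the hurdle depends on the margin. With 21 per arm, the observed difference needed is about 1.19 under the literal +0.5 boundary, stricter than printed, or about +0.19 under −0.5, less strict. The power statement must be redone as well. Under −0.5, power at a true difference of 0 is about 31–36%. Under +0.5, 80% power needs a true difference of about 1.45 (21 per arm) or 1.37 (25 per arm). The stated 80% cannot stand without a stated true difference to support it.
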